5 STUDY ENDPOINTS

5.1 Primary Endpoint(s)

The primary endpoint is overall study success at 3 years postoperative. Success is defined the same way it was in the PMA cohort, to allow comparison. The primary endpoint will be analyzed using the exact binomial test. Overall success is defined as:

- No component revision,
- Modified Harris Hip Score (mHHS) of at least 80 points, and
- No radiographic failure, defined as:

No radiolucencies greater than 2 mm in 50% or more in any of the cup or stem zones, no femoral or acetabular subsidence greater than or equal to 5 mm from baseline, and no acetabular cup inclination changes greater than 4 degrees from baseline when accompanied by "Mild", "Moderate", "Marked" or "Disabled" mHHS pain score.

In the event that the need for remote visits due to COVID-19 significantly impacts the primary endpoint, the following additional analyses will be performed to allow inclusion of as many study subjects as possible in the analysis:

- (1) An alternative analysis in which overall success will consist of components that can be remotely collected via telephone, and will be defined as:
 - No component revision,
 - Patient portion of the Modified Harris Hip Score (mHHS), as described in Section 3.2.4**Error! Reference source not found.**, of at least 80 points.
- (2) An alternative analysis that allows for post-three-year data to be used in place of missing or incomplete three-year visits ("rollback").

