7.3 Handling of Missing, Incomplete and Repeat Data

When data are being summarized, only the non-missing values will be evaluated for computing summary statistics.

In general, partial dates will be imputed as follows:

- if only the day is missing, the first day of the month will be assumed;
- if the day and the month are missing, January 1st will be assumed;
- if a date is completely missing or unknown and the visit is not indicated on the CRF, the data will not be included in a specific time window for analysis. Note that all AEs will be included regardless of whether the date is missing or incomplete.

When subjects do not attend an in-office study visit and a telephone visit is conducted instead, the data from telephone visit will be used for analyses wherever possible.

When the patient misses the final (3 year) visit but is able to return the office at a later date, the additional mHHS and radiographic data that were not collected during the telephone visit will be collected and used for the final analyses at 3 years.

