7.6 Disposition Data

Patient accounting will be presented according to the recommendations in the FDA guidance entitled "Clinical Data Presentations for Orthopedic Device Applications".

- **Actual A (in window):** Hips with all data (Adverse Event/Revision Assessment, modified Harris Hip Score and radiographic evaluation) at the relevant visit, in the window time frame.

CONFIDENTIAL AND PROPRIETARY

This document contains information that is confidential and proprietary to Smith & Nephew PLC and Smith & Nephew, Inc. and is intended for use only by Smith+Nephew and its manufacturer. It shall not be reproduced or copied in whole or in part, nor shall the contents be disclosed by any means without prior written permission from Smith+Nephew, nor shall anyone make any use of it that is contrary to the expressed or implied wishes of Smith+Nephew.

Statistical Analysis Plan

Post-Approval Study of the R3™ Biolox® delta Ceramic Acetabular System – United States

Number: 16-4565-10
ST: 1176
Version: 5.2, 19-JAN-2024
Page: 16 of 22

- **Actual A:** Hips with all data (Adverse Event/Revision Assessment, modified Harris Hip Score and radiographic evaluation) at the relevant visit (includes hips with visits out of the interval window).
- **Actual B:** Hips who returned to the office with any data (Adverse Event/Revision Assessment, modified Harris Hip Score or radiographic evaluation) at the relevant visit.
- **Actual Modified B:** Hips with any data (Adverse Event/Revision Assessment, modified Harris Hip Score, radiographic evaluation, or telephone visit) at the relevant visit, including hips unable to return for follow-up visits that were contacted by telephone for determination of patient satisfaction and device survival.
- **Theoretical:** Number of hips that would have reached the beginning of the study window associated with each visit if all subjects returned.
- **Deaths:** Cumulative number of subjects that died during or prior to the upper window limit of the study visit.
- **Failures:** Cumulative number of hips that failed (revision) during or prior to the upper window limit of the study visit.
- **Expected:** Theoretical hips minus the number of deaths and revisions.
- **Follow-up Rate:** Actual/Expected*100

Patients discontinued from the study prematurely will be presented, with a breakdown of the reasons for discontinuation as reported in the CRF.

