7.10 Analysis of Primary Endpoint(s)

The primary endpoint is overall study success at 3 years postoperative. Success is defined the same way it was in the PMA cohort, to allow comparison. Overall success is defined as:

- No component revision,
- Modified Harris Hip Score (mHHS) of at least 80 points, and
- No radiographic failure, defined as:

No radiolucencies greater than 2 mm in 50% or more in any of the cup or stem zones, no femoral or acetabular subsidence greater than or equal to 5 mm from baseline, and no acetabular cup inclination changes greater than 4 degrees from baseline when accompanied by "Mild", "Moderate", "Marked" or "Disabled" mHHS pain score.

All subjects in the enrolled population with evaluable data at 3 years postoperative will be considered for analysis. Subjects lost to follow up due to revision at any point up to the end of the three-year visit window will be considered as failures.

A one-sided analysis using the exact binomial model will be used to analyze success rate against the success rate of the PMA cohort of 86.4%, with 8% margin (as per Sample Size Section 6.1).

As mentioned in Section 7.14 additional analyses will be performed to accommodate inclusion of as many study subjects as possible in the analysis.

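### The rollback analysis in SAP 5.1 is worded at visit level, so it permits a subject already settled as an in-window failure to be rescored as a success from a later visit

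*SAP*

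**What the plan says.** SAP 5.1 defines 3-year success as the joint absence of revision, an mHHS of 80 or more, and no radiographic failure. It then provides two additional analyses under a condition: "In the event that the need for remote visits due to COVID-19 significantly impacts the primary endpoint". No threshold is given for that condition. The second analysis is the rollback: "An alternative analysis that allows for post-three-year data to be used in place of missing or incomplete three-year visits". SAP 5.1 does not define an incomplete visit and sets no limit on how late the replacement data may be.

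Four other places bear on it:

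- **SAP 7.6** shows what a complete visit contains. The Actual A category is "Hips with all data (Adverse Event/Revision Assessment, modified Harris Hip Score and radiographic evaluation) at the relevant visit". A visit lacking any one of these is not complete.
- **SAP 7.10** fixes one kind of failure: "Subjects lost to follow up due to revision at any point up to the end of the three-year visit window will be considered as failures". It has no matching sentence for a failed mHHS or a failed film. Its analysis set is "All subjects in the enrolled population with evaluable data at 3 years postoperative will be considered for analysis", and evaluable is not defined.
- **SAP 7.3** covers the subject who misses the final visit and comes to the office later: "the additional mHHS and radiographic data that were not collected during the telephone visit will be collected and used". This adds what the telephone contact could not supply.
- **SAP 3.2.4** lets a full mHHS replace the telephone patient portion when the subject attends the office within the same interval.

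**The concern.** Because all three components must be met, one failed component decides the outcome whatever else is missing. Take a subject with an in-window office mHHS of 74 and no film. The criterion is "Modified Harris Hip Score (mHHS) of at least 80 points", so this subject is a 3-year failure, yet the visit is incomplete. If a later visit gives an mHHS of 82 and a clean film, putting that visit in place of the 3-year visit scores a success. The same can happen with an in-window film showing subsidence of 5 mm or more and no mHHS, if the later reading is below 5 mm.

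The stated purpose of the additional analyses is to bring in as many subjects as possible. These subjects do not need rescuing, because their 3-year status can already be determined. There is also an asymmetry. An incomplete visit can be a known failure but never a known success, so among subjects whose status is settled the replacement can only turn failures into successes. Films are the item the SAP itself expects to be missing or out of window (7.6 and 7.14), so a visit with a score and no film is a foreseeable case. Two programmers could classify such a subject differently, with the late result already in view.

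**Working it through.** **1. Reproduce the plan's figures.** Inputs from SAP 6.1 and 7.10: reference rate 0.864, margin 0.08, one-sided alpha 0.05, power 80%, exact binomial test.

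- Null rate: 0.864 − 0.08 = 0.784.
- The smallest n with exact power of at least 80% is 146. The pass line is 123 successes: P(X ≥ 123 | 146, 0.784) = 0.0492, and power at 0.864 is 0.8125.
- Allowing for 20% loss: 146 / 0.80 = 182.5, so 183.

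Both stated sample sizes reproduce. None of the plan's figures is in dispute.

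**2. Does any passage lock an in-window failure?**

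| Situation | Provision | In-window failure kept? |
|---|---|---|
| Revision by end of 3-year window | SAP 7.10 | Yes |
| Visit missed, telephone contact, later office visit | SAP 7.3 | Late data are added to what is missing |
| In-window office mHHS below 80, no film | SAP 5.1 rollback only | Not stated |
| In-window radiographic failure, no mHHS | SAP 5.1 rollback only | Not stated |

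**3. How often might a score cross 80 on repeat?** The documents give no score distribution and no counts, so these are assumptions: mHHS normal with mean 91 and SD 10, correlation r between on-time and late scores from 0.7 to 0.9, late films clean, and 20 incomplete visits that do have an mHHS. The threshold is z = (80 − 91)/10 = −1.1, so 13.6% score below 80.

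| r | P(late ≥ 80, given on-time < 80) | P(late < 80, given on-time ≥ 80) |
|---|---|---|
| 0.7 | 0.493 | 0.077 |
| 0.8 | 0.403 | 0.063 |
| 0.9 | 0.286 | 0.045 |

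Known failures among the 20 visits: 20 × 0.136 ≈ 2.7.

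- Failure to success: 20 × 0.136 × 0.493 ≈ 1.34 at r = 0.7, and 20 × 0.136 × 0.286 ≈ 0.78 at r = 0.9.
- Pass to fail: 20 × 0.864 × 0.077 ≈ 1.33 at r = 0.7 (1.34 before rounding the inputs), and 20 × 0.864 × 0.045 ≈ 0.78 at r = 0.9.

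If late returns are unselected, the expected net change is zero. A bias arises only if the chance of a late return depends on the on-time score or on later improvement.

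**4. Worst case for the rollback analysis.** Suppose k failures become successes with no change the other way. At n = 146 and a true rate of 0.784, the pass probability is P(X ≥ 123 − k):

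| k | Pass probability |
|---|---|
| 0 | 0.0492 |
| 1 | 0.0753 |
| 2 | 0.1104 |
| 3 | 0.1553 |

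One subject can decide the rollback result: 122 successes miss (p = 0.0753) and 123 pass (p = 0.0492). These figures do not follow from step 3. They ignore the reverse changes, k = 3 exceeds the 2.7 known failures there, and step 3 has 13.6% scoring below 80 whereas the pass probability is taken at a failure rate of 1 − 0.784 = 21.6%.

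**The case against.** The strongest reply is that this is an ambiguity and not an instruction. The sentence allows late data to be used; it does not order that on-time results be discarded. SAP 7.3, whose title covers missing and incomplete data, already fills gaps for late 3-year returns, and the final accountability rule in SAP 7.6 combines a telephone or full score with an out-of-window film. Reading 5.1 in that spirit is natural. This stands in part: a reader who inferred that the SAP requires failures to be overwritten would go beyond the text. But 7.3 addresses a missed visit with a telephone contact, not an incomplete office visit. The 7.6 rule governs accountability counts, not endpoint scoring. SAP 5.1 refers to neither for this purpose.

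Second, rollback is supplementary and conditional, and the formal test is in 7.10. This stands in full. A reader might take the 7.5% to 15.5% figures as inflation of the study's type I error; they are not.

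Third, nothing shows that late returns are selected by score. SAP 7.6 promises every effort to obtain late films and full scores, without regard to the result. This also stands: the documents give no evidence of selection, though they contain no rule that makes the analysis indifferent to it.

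Fourth, replacing an observed score is not peculiar to 5.1. SAP 3.2.4 does so for a telephone score within the same interval, and 7.6 takes the full score where available. So a remedy saying only that an in-window mHHS stands would leave the telephone score, probably the commonest case, unresolved or in conflict with those sections.

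**Conclusion.** The concern holds as a defect in the wording of a supplementary analysis. SAP 5.1 permits a settled in-window mHHS or radiographic failure to be rescored as a success from a later visit, and no other section prevents it. Revisions up to the end of the 3-year window are protected by 7.10.

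The size cannot be fixed from the documents, which do not say how many visits were incomplete or who returned late. Under the stated assumptions, about 0.8 to 1.3 known failures per 20 incomplete visits with a score would cross to success, matched by equal expected movement the other way if returns are unselected. The pass probabilities of 7.5%, 11.0% and 15.5% bound what one, two or three unopposed changes would do to the rollback analysis alone. The formal test keeps its exact size of 4.9% as far as this sentence is concerned. The case for changing the text rests on the fact that a settled outcome should not depend on whether the subject was brought back late, and not on a demonstrated bias.

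**What to change.** Reword the rollback in SAP 5.1 at component level:

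- Post-three-year data fill only components with no in-window result.
- An in-window office mHHS, and an in-window film, stand whether they pass or fail.
- A subject who fails any such component in window remains a failure.

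Two further points should be stated in the same place. First, say whether an in-window telephone patient-portion score stands or is replaced by a later full mHHS, and make this agree with 3.2.4, 7.3 and 7.6. Second, say which visit's pain answer is paired with a late film for the inclination criterion.

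The cost is one or two sentences and a small programming change, with no new data. The rollback success rate may be slightly lower.

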5.2 Secondary Endpoint(s)

Secondary endpoints include clinical assessments of pain and function using the modified Harris Hip Score, radiographic findings, and implant survivorship.

5.3 Exploratory Endpoint(s)

There are no exploratory endpoints for this study.

CONFIDENTIAL AND PROPRIETARY

This document contains information that is confidential and proprietary to Smith & Nephew PLC and Smith & Nephew, Inc. and is intended for use only by Smith+Nephew and its manufacturer. It shall not be reproduced or copied in whole or in part, nor shall the contents be disclosed by any means without prior written permission from Smith+Nephew, nor shall anyone make any use of it that is contrary to the expressed or implied wishes of Smith+Nephew.

Statistical Analysis Plan

Post-Approval Study of the R3™ Biolox® delta Ceramic Acetabular System – United States

Number: 16-4565-10
ST: 1176
Version: 5.2, 19-JAN-2024
Page: 13 of 22

5.4 Safety Endpoint(s)

Adverse events and device deficiencies, noted by study staff and reported by the subject, and occurring from the time of study device implantation through to study completion should be recorded on the appropriate CRFs.

6 STATISTICAL CONSIDERATIONS

6.1 Determination of Sample Size

The primary objective of this study is to confirm that the safety and effectiveness of the R3 Biolox delta Ceramic Acetabular System in the US population is consistent with the effectiveness and safety profile shown in the European study (PMA cohort). The primary endpoint is overall study success at 3 years postoperative. Secondary endpoints include clinical assessments of pain and function, radiographic findings, and implant survivorship.

Overall success (as defined in the section entitled "Primary endpoint") in the PMA Cohort was found to be 86.4% at 3 years postoperative for the Biolox delta ceramic-on-ceramic (DOD) treatment group. It is expected that the overall success for the DOD US Cohort is similar to the overall success for the DOD PMA Cohort (European data).

Statistical Hypotheses:

$$H_0: \pi_{DOD} - 0.864 \leq \delta$$

$$H_a: \pi_{DOD} - 0.864 > \delta$$

Where,

π_{DOD} = Overall Success of DOD US

1-sided alpha error = 5%

Power of the test = 80%

$\delta = -0.08$

The minimum sample size required for hypothesis testing: 146 DOD US subjects. The total sample size after adjustment for lost-to-follow-up (20%) is 183 DOD subjects. Sample size was calculated assuming use of an Exact Binomial test³.

³ https://support.sas.com/documentation/cdl/en/statug/63962/HTML/default/viewer.htm#statug_power_a0000000996.htm

CONFIDENTIAL AND PROPRIETARY

This document contains information that is confidential and proprietary to Smith & Nephew PLC and Smith & Nephew, Inc. and is intended for use only by Smith+Nephew and its manufacturer. It shall not be reproduced or copied in whole or in part, nor shall the contents be disclosed by any means without prior written permission from Smith+Nephew, nor shall anyone make any use of it that is contrary to the expressed or implied wishes of Smith+Nephew.

Statistical Analysis Plan

Post-Approval Study of the R3™ Biolox® delta Ceramic Acetabular System – United States

Number: 16-4565-10
ST: 1176
Version: 5.2, 19-JAN-2024
Page: 14 of 22

6.2 Randomization

This is a non-randomized device trial.

6.3 Interim Analysis

An interim data release will occur at the midpoint of the study, 2.5 years after study initiation. The interim data release will be comprised of data regarding secondary endpoints. In addition, an interim report will be provided to the Agency annually, which will include summaries of the current data in the study.

7 STATISTICAL ANALYSIS

7.1 General

Categorical variables will be summarized with the number and percent of subjects in each group. Continuous variables will be summarized with the mean, standard deviation, median, minimum, and maximum values. 95% confidence intervals will be calculated for the primary and secondary endpoints.

All data collected in the CRF will be presented in the listings.

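### Does a 95% confidence interval beside a one-sided 5% test give the primary endpoint two conflicting answers?

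*SAP*

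**What the plan says.** The test is defined in two places. SAP 6.1 (and Protocol 9.2) gives the hypotheses, a difference limit of -0.08, and "1-sided alpha error = 5" per cent. It takes its reference from the European data: overall success "in the PMA Cohort was found to be 86.4% at 3 years postoperative". SAP 7.10 then says: "A one-sided analysis using the exact binomial model will be used to analyze success rate" against that reference, and takes the margin from 6.1. The bar is therefore 0.864 - 0.08 = 0.784.

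The interval appears elsewhere. SAP 7.1 General, in the same terms as Protocol 9.1, says that "95% confidence intervals will be calculated for the primary and secondary endpoints". The sentence follows the rules for counts, percentages, means and standard deviations. Neither document states whether the interval is one- or two-sided, which method is used, or how it relates to the test. SAP 7.10 does not mention an interval. SAP 7.11 says the secondary endpoints, which share the interval sentence, will only be summarised descriptively.

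**The concern.** A one-sided exact test at 5% is equivalent to asking whether the one-sided 95% Clopper-Pearson lower bound, which is the lower limit of the two-sided 90% interval, lies above 78.4%. A 95% interval in the usual two-sided sense has a lower limit that corresponds to 2.5%. The plan therefore seems to put the same question at two error levels.

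Non-inferiority results are often read by setting the interval against the margin. In a post-approval study required by the FDA, the final report could reject the null hypothesis while its own interval includes success rates more than 8 points below the PMA cohort. If nobody had said in advance which of the two governs, settling it after the data were known would look opportunistic.

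**Working it through.** **Inputs** (SAP 6.1 and 7.10; Protocol 9.2): reference rate 0.864; margin 0.08, so p0 = 0.784; planned true rate p1 = 0.864; one-sided alpha 0.05; power 0.80; 146 evaluable subjects; 183 in total after 20% loss. Assumption: the 95% interval is two-sided. Clopper-Pearson is used first because it matches the exact test.

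**1. The plan's own figure.** The normal approximation gives

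n = [(1.645 × √(0.784 × 0.216) + 0.842 × √(0.864 × 0.136)) / 0.08]² = 145.6, so 146.

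The exact binomial search agrees: 146 is the smallest n with power of at least 80%. The test passes from 123 successes, with P(X ≥ 123 | 146, 0.784) = 0.0492 and P(X ≥ 123 | 146, 0.864) = 0.8125. Allowing for loss, 146 / 0.80 = 182.5, so 183. The sample size is reproduced, and it rests on the 5% one-sided test.

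**2. Test and interval side by side at n = 146.**

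| Successes | Rate | One-sided p | Two-sided 95% lower limit | Two-sided 90% lower limit | Probability if true rate is 0.864 |
|---|---|---|---|---|---|
| 122 | 83.6% | 0.0753 | 0.7654 | 0.7767 | 0.0553 |
| 123 | 84.2% | 0.0492 | 0.7731 | 0.7843 | 0.0685 |
| 124 | 84.9% | 0.0308 | 0.7808 | 0.7919 | 0.0807 |
| 125 | 85.6% | 0.0183 | 0.7886 | 0.7995 | 0.0903 |

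The test passes and the 95% lower limit is below 0.784 at two counts only, 123 and 124. The 90% lower limit agrees with the test in every row.

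**3. How often.** P(X = 123 or 124 | 146, 0.864) = 0.0685 + 0.0807 = 0.149, about 1 trial in 6.7. As a share of passing trials it is 0.1492 / 0.8125 = 18%. It equals the power of the 5% test minus the power of a 2.5% test: 0.8125 - 0.6633 = 0.1492.

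**4. How firm that figure is.** With the exact interval, by evaluable n:

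| n | 138 | 142 | 145 | 146 | 147 | 150 | 160 | 170 | 183 |
|---|---|---|---|---|---|---|---|---|---|
| Probability | 8.1% | 16.1% | 7.9% | 14.9% | 15.2% | 7.5% | 6.6% | 12.8% | 10.0% |

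The jumps come from the discreteness of the binomial. At n = 146 the Wilson and Agresti-Coull intervals also give 14.9%; the Wald and Jeffreys intervals give 6.8%, because only 123 conflicts.

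**5. What a matched interval would alter.** With the one-sided 95% bound as the rule, a trial passes at 123 (0.7843) and fails at 122 (0.7767), exactly as under the test. Alpha stays at 0.0492 and power at 81.2%. The chance of 123 or 124 successes when the true rate is at the bar is 0.0492 - 0.0183 = 0.0309, which is already part of the 5% that the design accepts.

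Making the two-sided 95% limit the rule would be a different design: pass from 125, alpha 0.0183, power 66.3%, and 181 evaluable subjects to reach 80% power.

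**The case for a change.** The best case for a change is that it costs one sentence and removes a foreseeable awkwardness. The sidedness and method of the interval are unstated, and at 124 of 146 the method decides whether the lower limit clears 78.4%. The study exists to show a regulator that US results match the European ones, and a regulator may well look at the interval first. A reader who judged by it would in effect be using a test with 66.3% power in place of 81.2%.

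The facts in this stand. The plan does not describe the interval, and a passing result with a lower limit under 78.4% is a realistic outcome.

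The inference that the plan has no order of precedence does not stand. SAP 7.10 gives one primary analysis, SAP 6.1 gives its error level, and the interval is named only in the general summary rules. Reading the interval against the margin is a convention that the reader brings; neither document asks for it. Nor is the discrepancy a sign of a faulty result: a gap of this kind arises whenever a one-sided 5% test is shown beside a two-sided 95% interval. Only the lower limit falls short, by 1.1 points at 123 successes and 0.3 at 124, and the observed rates there are 84.2% and 84.9%.

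**Conclusion.** The observation is correct but calls for no change to the plan. Followed as written, the plan gives a sound exact test at its stated level and a valid interval that shows precision at the customary 95%. A matched interval would leave alpha, power, sample size and the outcome at every possible count as they are. Even with it, the two-sided 95% interval could still be shown as a descriptive statistic, which is in practice how the plan already uses it.

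The 14.9% holds for 146 evaluable subjects, a true rate of 86.4% and a two-sided exact, Wilson or Agresti-Coull interval; the range over the settings checked is 6.6% to 16.1%. It is the chance that two different summaries straddle the bar, and it is not an error rate. If the 95% interval were read as a one-sided bound, which the wording also allows, it would be zero with the exact method. The conclusion rests on SAP 7.10 being the only decision rule, and nothing in either document contradicts that. An analyst writing the report would name the interval method and say that the test determines success.
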